Cerebrovascular Blood Flow	Doppler Ultrasound	meters per second (m/s)	CON	-5, 20	2	Mechanistic
			SMS	-120, -5, 20	3	
Middle Cerebral Artery Velocity	TCD	Centimeters per second (cm/s)	CON	Continuous	1	Mechanistic
			SMS	Continuous	1	
Static Cerebral Autoregulation	TCD	Unitless. Refers to MAP and CBF under steady state conditions that can be observed over a period of time ²⁶	CON	Continuous	1	Mechanistic
			SMS	Continuous	1	
Baroreflex Sensitivity	NIBP	Sensitivity: BRS is defined as the change in heart rate variability in milliseconds per unit change in BP	CON	Continuous	1	Mechanistic
			SMS	Continuous	1	
Heart Rate Variability (HRV)	NIBP	milliseconds (ms)	CON	Continuous	1	Mechanistic
			SMS	Continuous	1	
Heart Rate	NIBP	Beats per minute	CON	Continuous	1	Mechanistic
			SMS	Continuous	1	
Peripheral blood pressures (SBP, DBP)	VICORDER®	Millimeters of Mercury (mmHg)	CON	-5, 0, 5, 10, 15, 20, 25	7	Mechanistic
			SMS	-115, -15 0, 5, 10, 15, 20, 25	8	
Tissue Saturation Index	cwNIRS-SRS	Relative changes in TSI. Data will be presented as percent changes.	CON	Continuous	1	Mechanistic
			SMS	Continuous	1	
Venous Pooling in the Gastrocnemius	cwNIRS-SRS	This is a physiological response to prolonged sitting. It is quantified using the NIRS-SRS device by recording levels of tHb at the gastrocnemius	CON	Continuous	1	Mechanistic
			SMS	Continuous	1	

DEVICE 1: VICORDER®

PWV is calculated by dividing arterial path length (L) by the pulse transit time (TT) between a proximal and distal arterial segment. Measurements for L are acquired by recording the straight line distance between the proximal and distal cuff, per manufacturer guidelines. For PWV measures including the carotid artery, the straight line distance from the carotid artery to the sternal notch is included in calculations for L.

Transit time is calculated by the Vicorder software's proprietary algorithm that measures the time between the foot of the proximal pressure waveform to the foot of the distal pressure waveform. Pressure waveforms will be simultaneously captured using volume displacement cuffs. A small balloon cuff is placed over the carotid artery. The balloon used to generate the carotid pulse wave does not cause discomfort as it inflates to sub-diastolic blood pressure (~50 mmHg).

DEVICE 2: Transcranial Doppler

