- Validate the subject's compliance with pre-testing behavioral restrictions for the purpose of internal validity:
 - Waking up at similar times on the mornings of both experimental session

DEVICES 7 & 8: Data Acquisition (PowerLab) and Data Processing (LabChart)

For the TCD and NIBP, devices, data acquisition and processing will be automated using the accompanying software.

[figure not shown]
For the two test devices, the PowerLab data acquisition system (PowerLab 30 series, ADInstruments, CO, USA) will be used to simultaneously acquire signals from each device and from ECG.

LabChart 8 (ADInstruments) will record and process the data acquired using PowerLab. The ECG signal does not require any post-processing, the software filters ensure a distinct R peak. The foot of the pressure waveforms from the NIBP and PPG devices will be identified using a standard second derivative function. Offline, a custom macro will identify the peak of the R wave and the peak of the second derivative of each pressure waveform, then calculate the time between said peaks.

Cognitive Measurement 1: Trails A+B Tests

Test Structure & Application

The Trail-Making Test – Part A, the circles are numbered 1 – 25, and the subject will draw lines to connect the numbers in ascending order. Part B presents numbers and letters placed in a semi-random fixed order, in such a manner to avoid overlapping lines being drawn. The subject will connect 25 encircled numbers and letters in numerical and alphabetical order, alternating between the numbers and letters. For example, the first number “1” is followed by the first letter “A” followed by the second number “2” then second letter “B” and so on²³ Results for both TMT A and B will be reported in seconds.

Cognitive Measurement 2: Verbal Fluency Task

Test Structure		Application	
Tests of verbal fluency evaluate an individual's ability to retrieve specific information within restricted search parameters ²⁴ . The two subtests are (1) semantic fluency, and (2) phonemic fluency. The total number from each test will be summed and equate to the subjects' cognitive performance.		Verbal Fluency Test	
Phonemic fluency		Rapid generation of words beginning with a specific letter. Typically, F, A, and S are used as stimulus letters.	Instructions
Semantic fluency		Rapid generation of words from within a semantic category. "Animal names" and "supermarket items" are commonly used.	

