3 MEASUREMENT DEVICES

[figure not shown]
[figure not shown]
Device 1: VICORDER®

Device		
 Company: SMT Medical Model: VICORDER®: Arterial Stiffness Model Location: Wurzburg, Germany Oscillometric cuffs inflate at sub-systolic pressures to detect changes in the pressure waveform. Different sized cuffs are available.
Example Set-up		
 The cuffs can be placed on any 2 arterial segments. In the figure to the left, pressure cuffs placed over the brachial and femoral arteries. A small balloon is placed over the carotid artery to obtain a measurement for cfPWV. A low pressure (50 mmHg) is used for this site with minimal discomfort.
Raw Data		
 Top display = pressure waveform from proximal arterial segment Bottom display = pressure waveform from distal arterial segment Intrinsic software automatically detects the foot of the waveform of each arterial segment
Data Analysis		
 A = Site of proximal artery B = Site of distal artery Pulse wave velocity (PWV) = distance (D) / transit time (TT) Straight line distance (L) = Distance between two cuffs as measured according to manufacturer guidelines

[figure not shown]
[figure not shown]
		
 Transit Time (ΔT or TT) = Time between foot of proximal and distal waveforms. Oscillometric pressure waveforms will be determined at the brachial artery of the non-dominant arm using the VICORDER® in order to determine brachial and central arterial blood pressures.
Data Reduction		
 L is plugged into software prior to measurement. TT is averaged across 3 waveforms, and used to calculate one PWV Process repeated 3 times, for 3 PWVs per measurement cycle. Closest 2 PWVs averaged and used as outcome for measurement cycle.

[figure not shown]
Device 2: Transcranial Doppler (TCD)

Device		
 Company: Compumedics DWL Model: Transcranial Doppler Sonography TCD Location: Charlotte NC, USA DiaMon headset can be adjusted in 3 ways to accommodate each individual Connection between rear band and side panel sits behind the ear, below the occipital bone to ensure signal TCD probes should be in contact with head if headset has been fitted correctly

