Example Set-up		
 Ensure probe is positioned over the temporal window Apply ultrasound gel to probe and/ or temporal window Move probe until faint trace appears and then make further fine movements to increase trace of artery velocity

Raw Data		
 Signal quality is indicated by color: the more yellow, the stronger the signal Gain and depth adjust can be made in the signal window. Gain should sit between 38-44 for optimal signal output Typical velocities for middle cerebral artery (MCA) are ~80 cm/s-1, and ~60 cm/s-1 in older populations Typical depth for MCA is 45-55
Data Analysis		
 Using a custom macro, the software (Labchart) identifies the peak of the ECG R- wave and the peak of the second derivative of each pressure waveform (corresponds to foot), then calculate the transit time (TT) between said peaks. Pulse wave velocity (PWV) = distance (L) / TT
Data Reduction		
 Measures of brain PWV, MCA velocity, static CA and neurovascular coupling will be collected from this device are continuously recorded during a testing session Data reduction for this protocol will require the selection of 30s epochs at specific time points to observe how PS and MS are impacting measures of CVH In the picture to the left, a researcher selected a time period to report the data collected during this time. A strict protocol will be followed to ensure that selection of 30s epochs are synchronized amongst all measures and research participants to prevent bias.

Device 3: Non-Invasive Blood Pressure (NIBP)

Device		
 Company: ADInstruments Model: Human NIBP Nano System, Finapress Location: Sydney, Australia Single cuff contains an infrared photoplethysmographic (940 mmHg) sensor and inflatable cuff. PPG sensor continuously captures the pulse waveform. Inflatable cuff used to calibrate waveform Height correction unit corrects for hydrostatic pressure changes due to change in hand position relative to the heart.
Example Set-up		
 Device placed between distal and proximal inter-phalangeal joint of the index finger. Wrist apparatus is strapped to the individual's non-dominant wrist
Raw Data		
 Data captured using a data acquisition system (PowerLab). Also displayed are electrocardiogram (ECG) signals captured by PowerLab.

[figure not shown]

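### Brain PWV, a primary outcome, is timed from the ECG R-wave as the plan is written, so a change in cardiac timing can appear as a change in arterial stiffness

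*Combined protocol and SAP*

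**What the plan says.** Brain PWV and brachial-femoral PWV are the two primary outcomes (Protocol Synopsis; section 4.1). The Synopsis hypothesis is framed in terms of arterial stiffness, including cerebral stiffness.

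**Brain PWV.** In section 3, Device 2 (Transcranial Doppler), Data Analysis, the macro "identifies the peak of the ECG R- wave and the peak of the second derivative of each pressure waveform". The text equates the second-derivative peak with the waveform foot and takes the interval separating the two landmarks as transit time. The formula is then given: "Pulse wave velocity (PWV) = distance (L) / TT". Section 2.5, Devices 7 & 8, repeats the timing rule, which is to "identify the peak of the R wave and the peak of the second derivative of each pressure waveform, then calculate the time between said peaks". That section names the signals as follows: "The foot of the pressure waveforms from the NIBP and PPG devices will be identified using a standard second derivative function". The Doppler velocity trace is not among them.

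**VICORDER PWV.** Section 2.5, Device 1, states: "PWV is calculated by dividing arterial path length (L) by the pulse transit time (TT) between a proximal and distal arterial segment". Its software "measures the time between the foot of the proximal pressure waveform to the foot of the distal pressure waveform". Section 3, Device 1, defines transit time as "Time between foot of proximal and distal waveforms".

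For brain PWV the documents give no proximal arterial site, no path length, no subtraction of one R-to-foot time from another, and no measure of the delay before ejection. Section 4.2 gives the mechanistic outcomes, which include heart rate and heart rate variability, a descriptive and discussion role. It names no adjustment of brain PWV for cardiac timing.

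**The concern.** The R-wave is an electrical event in the heart, not an arterial waveform. The interval from it to a downstream foot is the delay before ejection plus the arterial transit time. Dividing a path length by that sum gives an arrival measure in m/s units, which is not velocity between two arterial sites.

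Two consequences follow. A change in the delay moves the reading when stiffness has not changed, and the fixed part of the delay shrinks any real change in percentage terms.

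This matters because both exposures could plausibly act on the heart. Section 1 describes blood pooling in the legs during sitting and neurohormonal activation under stress. Sitting lasts 20 minutes in CON and 2 hours in SMS (section 2.3, Experimental Visits), so a timing shift related to sitting need not cancel in the crossover contrast. At stake is whether a difference in this primary outcome can be read as cerebral arterial stiffness.

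**Working it through.** **The plan's own figures.** The plan gives no planning figure for brain PWV. Its only design figure is about 18 participants, based on aortic PWV (section 4.6). Take 1.25 m/s as the SD of the within-person difference, a change of 1 m/s, and one-sided 5% for each error. Then n = (1.25 × (1.645 + 1.645) / 1)² = 16.9, so 17, or 19 with the t distribution. The figure of 18 is reproduced closely on that reading, and the timing point does not alter it.

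**Inputs for the illustration.**
- 7.5 m/s and a change of 1 m/s: section 4.6, given there for aortic PWV and borrowed here only as a scale.
- Path length L of 0.2-0.5 m, delay before ejection D of 60-120 ms, and shifts in D of 5 and 10 ms: assumptions, not in the documents.

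**Formulae.** Arterial transit = L / PWV. Measured interval = D + L / PWV. Apparent PWV = L / (D + L / PWV). The percentage change is the old interval divided by the new one, minus 1.

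**Step 1: what a real change does to the timing.** Going from 7.5 to 8.5 m/s shortens transit by L × (1/7.5 − 1/8.5) = L × 0.01569 s/m. That is 3.1 ms at 0.2 m, 4.7 ms at 0.3 m and 7.8 ms at 0.5 m. This step does not depend on D: a cardiac shift of the same few milliseconds would give the same reading.

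**Step 2: apparent values at the corners of the assumed range.**

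| L (m) | D (ms) | Interval (ms) | Apparent PWV (m/s) | True 7.5 to 8.5 | D shorter by 5 ms | D shorter by 10 ms |
|---|---|---|---|---|---|---|
| 0.2 | 60 | 26.7 + 60 = 86.7 | 2.31 | +3.8% | +6.1% | +13.0% |
| 0.2 | 120 | 26.7 + 120 = 146.7 | 1.36 | +2.2% | +3.5% | +7.3% |
| 0.5 | 60 | 66.7 + 60 = 126.7 | 3.95 | +6.6% | +4.1% | +8.6% |
| 0.5 | 120 | 66.7 + 120 = 186.7 | 2.68 | +4.4% | +2.8% | +5.7% |

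A true rise of 1/7.5 = 13.3% thus appears as 2.2-6.6%. With stiffness unchanged, a 5 ms shorter delay appears as 2.8-6.1% and a 10 ms shorter delay as 5.7-13.0%. A longer delay moves the reading the other way.

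**Step 3: other assumptions.** With L 0.15-0.30 m, PWV 5-10 m/s and D 60-100 ms, a 5 ms shorter delay gives about 3-7% and a 10 ms shorter delay about 7-15%. The conclusion does not rest on one set of values.

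**Step 4: resolution.** Section 2.5, Device 2, gives Doppler acquisition at 50 Hz, which is 1000/50 = 20 ms per sample. Device 3 gives 1000 Hz (1 ms) for the ECG and two test devices. A 20 ms step is coarse beside a transit of 26.7-66.7 ms and a target change of 3.1-7.8 ms. Averaging beats within the 30 s epochs would reduce random rounding error, but the plan does not say how the foot is located between samples.

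**The case against.** **The foot-to-foot definition belongs to the VICORDER.** A reader might infer that brain PWV breaks a plan-wide definition. The documents do not support that: both statements sit under Device 1, and Device 2 has its own rule. What stands is that the Device 2 rule, followed as written, does not isolate arterial transit.

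**The Device 2 text is unclear.** It speaks of pressure waveforms although transcranial Doppler records velocity, and section 2.5 ties the foot rule to NIBP and PPG. The wording could mean R-referenced feet at two sites, with the R-wave cancelling on subtraction. The figures could not be read in the text available and might show this. However, no subtraction, second site or path length is written down, so the rule needs rewriting on either reading.

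**Size relative to the target.** A reader might infer that a cardiac shift of 5-10 ms matches or exceeds the effect the trial is looking for. As a general statement that fails. The largest value (13.0%) is below 13.3%. At L = 0.5 m a 5 ms shift is smaller than the diluted true effect (2.8% against 4.4% at a 120 ms delay). The plan also sets no target for brain PWV.

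**Cancellation.** A reader might infer that bias between conditions is certain. CON also includes sitting, and both conditions receive the same seated stressor. No figure in the documents shows that cardiac timing differs after 2 hours rather than 20 minutes. The supported statement is that the bias need not cancel.

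**Conclusion.** The point holds as a limit on what brain PWV can show. On the plain reading of sections 2.5 and 3, this primary outcome is a pulse arrival measure that cardiac timing can move, while the hypothesis reads it as cerebral arterial stiffness.

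Bias within a condition requires cardiac timing to change between baseline and the later time points. Bias between conditions requires that change to differ between CON and SMS. The documents establish neither, and the direction is unknown.

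The sizes in the table rest on assumed path lengths and delays and on velocities borrowed from the aortic sample-size section. Within those ranges, cardiac shifts of a few milliseconds are of the same order as the timing change produced by a 1 m/s rise. The change is worth making before any data are reduced.

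**What to change.** 1. In section 2.5 (Devices 7 & 8) and section 3 (Device 2), state for brain PWV which waveform is used, how L is measured, and the start and end points of the transit time.
2. If only R-to-MCA-foot timing is available, report it as pulse arrival time and draw no cerebral stiffness conclusion from it alone.
3. Use foot-to-foot timing only if a proximal arterial waveform is already recorded on the same beats as the Doppler signal. The plan does not describe one. The carotid cuff is a VICORDER signal, used for carotid-femoral PWV at a few time points with the device's own timing algorithm.
4. Prespecify a sensitivity analysis that compares the change in R-to-MCA-foot time with the change in R-to-foot time of the simultaneous NIBP signal. State its limits: a shift common to both may be cardiac or may come from a shared central arterial segment, and the finger path adds its own change. It is not a pure cardiac correction.
5. Reconcile the 50 Hz Doppler acquisition with the timing resolution that this measure needs.

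**Cost.** Items 1, 2 and 4 need changes to wording and to the offline macro, with no new visits or devices. Item 5 may need a change to acquisition settings. The downside is a weaker label for a primary outcome and a sensitivity analysis that is noisier because it compares two timings.

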11.3	7814																																																																																																																																																																																																						
15.0	7807																																																																																																																																																																																																						
18.8	7800																																																																																																																																																																																																						
22.5	7793																																																																																																																																																																																																						

 Test duration: Approximately 5min Participant is in seated upright position At the beginning of the test, the researcher will call out a four digit number and ask the participant to subtract either 7 or 13 Correct responses will not be recorded as an outcome for this study 																																																																																																																																																																																																							

The MS used for this protocol is the Mental Arithmetic Test (MAT), a commonly used exam to impose a small psychological stimulus on the participant. This test will approximately last for five minutes. The researcher will call out a four-digit number and ask the participant to subtract either seven or 13. Correct responses will not be recorded as an outcome for this study. During this test a metronome will play at a pre-set tempo. The subjects will be required to conduct continuous subtraction with the tempo to the best of their ability. Every minute, a new four digit number will be called out and the participant must subtract the seven or 13 from the number.

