Brain PWV and Middle cerebral artery velocity (MCAv) will be measured using continuous bilateral TCD (ST3, Spencer Technologies). MCAv accounts for 70-80% of the brain's total perfusion²⁵. The data will be acquired continuously (50 Hz) using an analog-to digital convertor (PowerLab 30, ADInstruments).

DEVICE 3: Non-Invasive Blood Pressure (NIBP)

The PowerLab data acquisition system (PowerLab 30 series, ADInstruments, CO, USA) will be used to simultaneously acquire signals from each device and from ECG. A standard Lead II ECG will be recorded from three electrodes placed on the right and left shoulders, and just below the left rib. The signals from the ECG and two test devices will be sampled a frequency was 1000 Hz, providing a temporal resolution of 1ms.

DEVICE 4: Doppler Ultrasound

A commercial ultrasound device equipped with 11-3 MHz linear array probe will be used. Experimenters will assess blood flow in three cerebral arteries: common carotid, internal carotid, and vertebral.

DEVICE 5: Continuous Wave Near-Infrared Spectroscopy with Spatially Resolved Spectroscopy (cwNIRS-SRS or NIRS)

A continuous, non-invasive system to measure cerebral perfusion. The near-infrared spectroscopy probe used in this protocol emits a single frequency of light (cwNIRS) to monitor relative change in total hemoglobin. Using the spatially-resolved spectroscopy (SRS) technique, cwNIRS can estimate absolute measures of perfusion (e.g. total hemoglobin, tissue saturation index). The cwNIRS-SRS device will be positions on the forehead, approximately 3cm to the right of the center, directly over the eyebrow. An additional probe will be placed over the medial gastrocnemius to observe venous pooling of blood in the lower-limbs. The location of both probes will be marked to ensure identical placement for the next experimental session. The device will be covered with a dark opaque cloth to prevent signal contamination by ambient light as per manufacturer recommendations.

DEVICE 6: ActiGraph

An ActiGraph accelerometer will be distributed to the research participant at the conclusion of the familiarization session along with a sleep journal packet. The subject will be asked to record on the timeline when he/she began to sleep and awaken each day until the conclusion of his/her participation in this study. The device will be worn on the individual's non-dominant wrist according to manufacturer guidelines. The data collected from this device will be used for one purpose:

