Alternating fluency		Rapid generation of words by alternating between two semantically unrelated categories. "Fruit and furniture" are often used.	
Excluded-letter fluency		Rapid generation of words that do not contain a specified vowel (e.g., the letter "A").	

Cognitive Measurement 3: Memory Recall

Participants will be read word lists from the Hopkins Verbal Learning Test at the rate of 1 word every 2 seconds pre-test and post- cognitive testing period. The Hopkins Verbal Learning test word lists contain 12 words, 4 words from 3 semantic categories.

Cognitive Measurement 4: Brain Fog

Brain fog will be subjectively measured using a modified Borg Rate of Perceived Exertion (RPE) scale as there is no known reliable and valid objective measure of brain fog. This will be administered pre-test and post-cognitive testing period.

Data Reduction

The data collection periods are listed in Table 3. Minute values are noted in **Figure 1** and are expressed relative to the administration of the MAT.

Table 3. Data reduction methods for experimental protocol

Device	Outcomes	CON (min)	SMS (min)	Reduction
VICORDER®	bfPWV	-5, 0, 5, 10, 15, 20, 25	-115, -15, 0, 5, 10, 15, 20, 25	Measures done in triplicate. Closest 2 will be averaged for mean and variance reported
	cfPWV	-5, 25	-115, -15, 25	
	faPWV	-5, 25	-115, -15, 25	
	CBPs	-5, 0, 5, 10, 15, 20, 25	-115, -15, 0, 5, 10, 15, 20, 25	
	Peripheral BPs	-5, 0, 5, 10, 15, 20, 25	-115, -15, 0, 5, 10, 15, 20, 25	
	Augmentation index	-5, 0, 5, 10, 15, 20, 25	-115, -15, 0, 5, 10, 15, 20, 25	
TCD	Brain PWV	Continuous	Continuous	30s selections made by following a
	MCA velocity	Continuous	Continuous	

	Static cerebral autoregulation	Continuous	Continuous	prearranged protocol. Data for the outcome in the time epoch will be averaged and SD will be reported
	Neurovascular coupling	Continuous	Continuous	
NIBP	Baroreflex sensitivity	Continuous	Continuous	30s selections made by following a prearranged protocol. Data for the outcome in the time epoch will be averaged and SD will be reported
	Heart rate variability	Continuous	Continuous	
	Heart rate	Continuous	Continuous	
Ultrasound	Cerebrovascular BF	-5, 25	-120, -5, 20	
NIRS	Cerebral perfusion	Continuous	Continuous	30s selections made by following a prearranged protocol. Data for the outcome in the time epoch will be averaged and SD will be reported
	Tissue saturation index	Continuous	Continuous	
	Venous pooling	Continuous	Continuous	

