2.6 Timeline

Study Time Commitment

Stage	Time (mins)	Description
Recruitment	10	Via email, flyer and/or class presentation
Familiarization Session	35	Familiarize test subject with the purpose of the study, all experimental devices and the timeline of each experimental condition
Experimental Visits	255	All measurements, single visit
Total	300	

Familiarization Session	
Time (mins)	Action
0:00-5:00	Share adult consent form with participant. Questions and concerns will be heard on the protocol and purpose of this study.
5:00-10:00	Discuss the underlying physiology and purpose that lead to the creation of this study. Discuss how this study will answer the research questions.
10:00-30:00	The researcher will attach each device to the participant to familiarize him/her to the protocol . No data will be collected for later analysis during this period.
30:00-35:00	Subject and researchers will schedule the date and time for CON and SMS. ActiGraph will be attached to the research participant. A document will be provided detailing all behavioral restrictions (e.g. abstinence from caffeine, alcohol) and instructions on wearing the ActiGraph will be provided.
Session End – Total time spent in APL: 35 minutes	

[figure not shown]
CON Experimental Session			
Time (mins)	Action	Measurement Order	EXAMPLE START TIME
-30:00 - -25:00	Anthropometrics	Weight (kg) Height (cm) BMI (kg/m ²)	10:15 AM
-25:00	Begin Supine Rest	N/A	10:20 AM
-25:00 - -15:00	Affix devices to participant.	Path lengths (cm)	10:20 AM
-15:00	End Supine Rest. Begin continuous data collection from devices. Begin sitting period	TCD measures NIRS measures NIBP measures	10:30 AM
-15:00 - -5:00	Ultrasound data collection	Cerebrovascular blood flow (common carotid, internal carotid, and vertebral arteries)	10:30 AM
-15:00 - -5:00	VICORDER® data collection	bfPWV/A cfPWV/A faPWV/A	10:30 AM
-5:00-0:00	Mental Arithmetic Test	N/A	10:40 AM
00:00-1:00	VICORDER® data collection	bfPWV/A immediately after MAT	10:45 AM
5:00-20:00	VICORDER® data collection	bfPWV/A every 5m post-MAT for addition 20m	10:50 AM
25:00-30:00	VICORDER® data collection	All measures of PWV/A 10m post-MAT	11:10 AM
30:00-40:00	Cognitive tests	Trails A+B VFT	11:15 AM
Test End – Total time spent in APL: 75 minutes			

[figure not shown]
[figure not shown]
SMS Experimental Session

Time (mins)	Action	Measurement Order	EXAMPLE START TIME
-140:00 - -135:00	Anthropometrics	Weight (kg) Height (cm) BMI (kg/m ²)	8:25 AM

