[figure not shown]

- LabChart 8 can perform real time or offline function, including data averaging, peak detection, derivatives etc.

Data Reduction		
 • All measures collected from this device are continuously recorded during a testing session • Data reduction for this protocol will require the selection of 30s epochs at specific time points to observe how PS and MS are impacting measures of CVH • In the picture to the left, a researcher selected a time period to report the data collected during this time. • A strict protocol will be followed to ensure that selection of 30s epochs are similar amongst all measures and research participants to prevent bias.
-----------------------	--	---

Device 4: Doppler Ultrasound

[figure not shown]
[figure not shown]
[figure not shown]
Device		
 • Company: GE Healthcare • Model: Logiq P6 • Location: Chicago, IL • An 11L linear probe will be used for this protocol
---------------	--	---

Example Set-up		
 Measurement of blood flow through the carotid artery using a linear probe Probe is placed parallel to the blood vessel 10s videos of the common carotid, vertebral, and internal carotid arteries will be collected at each designated time point in the protocol Participants will be instructed to hold one's breath for the duration of the recording to ensure a clear video will be captured of the observed artery
Raw Data		
 Ultrasound videos are recorded at 30 Hz using an external video capture system Debut Professional (v4.0, NCH Software®) is used to record the present image on the Ultrasound device for later analysis Image to the left shows an example video captured by this software
Data Analysis		
 The captured videos will be analysed offline using specialized image analysis software (FMD Studio®,) shown to the left. The software measures and exports second-by-second diameters and blood velocities Cardiovascular Suite (Quipu, v3.5.3) analyzes raw ultrasound footage Coordination with ECG will produce measures of blood flow
Data Reduction		

[figure not shown]
- Lab-designed macro cleans raw data output generated by the video analysis software
- Macro is capable of calculating blood flow along with other measures that define the flow profile of the observed artery

[figure not shown]
[figure not shown]
[figure not shown]

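### Heart rate variability and baroreflex sensitivity are reduced to averaged 30-second epochs, and baroreflex sensitivity is defined on the wrong variable, although longer recordings will exist

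*Combined protocol and SAP*

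**What the plan says.** In Table 3 (section 2.5) the NIBP rows for BRS, HRV and heart rate share one reduction: "30s selections made by following a prearranged protocol. Data for the outcome in the time epoch will be averaged and SD will be reported". The Data Reduction row for Device 3 in section 3 repeats the epoch length: "Data reduction for this protocol will require the selection of 30s epochs at specific time points". It adds that a strict selection procedure will keep epochs comparable across measures and participants, to prevent bias. That procedure is not given.

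Table 2 states: "BRS is defined as the change in heart rate variability in milliseconds per unit change in BP". HRV is a separate outcome in the same table, in milliseconds, with no parameter named.

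The data available are longer than the epochs. Section 3, Device 3: "All measures collected from this device are continuously recorded during a testing session". The section 2.6 timelines place "Begin continuous data collection from devices" at −15 min in CON and −125 min in SMS. Section 2.5, Device 3, adds an ECG sampled at 1000 Hz: "A standard Lead II ECG will be recorded from three electrodes placed on the right and left shoulders". On the stressor, section 2.4 says: "This test will approximately last for five minutes".

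Table 2 and section 4.1 class HRV and BRS as mechanistic. Section 4.2 gives mechanistic outcomes a supporting role in discussing the responses. Table 4 reports them at Baseline, Post-PS and Post-MS.

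**The concern.** A rule that works for a level is applied to a spread and to a slope. Mean heart rate is stable over 30 s. HRV is the dispersion of beat intervals, so it needs enough beats and enough cycles of the slower rhythms, and averaging the data in an epoch does not produce it. If the SD to be reported is the SD of the R-R intervals, that would be a 30 s HRV value, but the plan does not say so.

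The BRS wording is a separate fault. BRS is the change in beat interval per unit change in pressure. HRV gives one dispersion value per epoch, so it has no beat-to-beat slope on pressure. An analyst who followed Table 2 literally would report something other than BRS.

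At stake is the autonomic part of the mechanistic account: with 20 participants, noisy or misdefined values may show nothing where a CON–SMS difference exists.

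**Working it through.** **Plan's own figure.** The plan gives no derivation for 30 s. Its only computed figure is about 18 participants (section 4.6), which concerns PWV. With one-sided 5%, 95% power and 1.25 m/s taken as the SD of the paired difference, n = (1.645 + 1.645)² × 1.25² / 1² = 16.9, or about 19 with t quantiles. That agrees with 18 and does not bear on this point.

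**Recording length.** CON: −15 to +40 min = 55 min. SMS: −125 to +40 min = 165 min.

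**Beats and cycles.** The example LabChart export in section 3 (Devices 7 & 8) shows 51.6 to 62.5 beats/min; 80 is my assumed upper value.
- 30 s: 51.6/2 = 26, 62.5/2 = 31, 80/2 = 40 beats. In 5 min at 51.6 to 62.5: 258 to 312.
- A 0.1 Hz rhythm completes 0.1 × 30 = 3 cycles in 30 s and 30 in 5 min. At 0.04 Hz: 1.2 and 12.

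**Independent beats, no spectral assumption.** CV of an SD = 1/√(2(n−1)).
- 30 s: n = 25.8 gives 14.2%; n = 31.25 gives 12.9%.
- 5 min: n = 258 gives 4.4%; n = 312.5 gives 4.0%.

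**Correlated beats, by simulation.** The documents give no R-R spectra, so these inputs are assumptions. Set A: 70–80 beats/min, three mixes of slow, 0.1 Hz and respiratory variation, 400 runs each. Set B: four scenarios, 1,500 series each, 60–75 beats/min; R-R SD components 20–30 ms (very low frequency), 20–25 ms (low) and 12–30 ms (high); BRS gain 8–12 ms/mmHg. SDNN is the SD of the intervals; RMSSD is the root mean square of successive differences. Sampling CV of one value:

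| Measure | A: 30 s | A: 5 min | B: 30 s | B: 2 min | B: 5 min |
|---|---|---|---|---|---|
| SDNN | 16–25% | 4–8% | 21–23% | 11–13% | 7–10% |
| RMSSD | 16–17% | 5% | 22–25% | 11–13% | 7–8% |
| Low-frequency power | – | – | 85% | 48–50% | 32–33% |
| BRS, sequence method | – | – | 26–33% | 13–17% | 8–10% |

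Mean SDNN from 30 s is 3–15% below the 5 min value across both sets; RMSSD (set B) is only 2–3% below. In set B a 30 s window yields 4–5 baroreflex sequences against 42–52 in 5 min. Of the 30 s windows, 12–25% hold fewer than three; no 5 min window does.

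BRS by regression (assumed gain 10 ms/mmHg, systolic SD 3 mmHg, unrelated R-R SD 15–30 ms) has SE 2.1–4.1 ms/mmHg from 30 s and 0.6–1.2 from 5 min.

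**What this means for n = 20.** Counting window sampling error only, the CON–SMS difference detectable at one time point with 80% power and two-sided 5% is (2.093 + 0.861) × √2 × CV / √20 = 0.934 × CV.
- BRS: 0.934 × 26.1% to 33.1% = 24–31% from 30 s; 0.934 × 7.8% to 10.3% = 7–10% from 5 min.
- RMSSD (set B): 20–24% against 7–8%.

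**The case against.** The case for leaving the plan alone has real content.

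- **Role.** Both outcomes are mechanistic, in a study the synopsis labels pilot testing, and section 4.2 directs the models at the primary and secondary outcomes. This stands and limits the weight of the point.
- **Number of epochs.** A reader might infer that each time level rests on a single 30 s value. The documents speak of several time points and do not say how epochs are combined. If six post-stress epochs (0 to 25 min, an assumption) were averaged and roughly independent, SDNN error would fall from 16–25% to 16/√6 to 25/√6 = 6.5–10%, close to the 5 min figures. This stands for Post-MS. Baseline and Post-PS may still rest on one epoch each, and averaging does not remove the SDNN shortfall.
- **False positives.** A reader might infer that the noise could create a spurious condition effect. It does not: random sampling error widens intervals without raising the type 1 error of a valid model, and the SDNN shortfall largely cancels when epochs are equally long in both visits.
- **ECG.** A reader might take the NIBP label in Table 2 to mean that HRV comes from the finger pulse although an ECG exists. Section 2.5 describes the ECG under the NIBP heading, and a macro already finds R peaks, so the label may simply mean that set-up. Only the wording needs settling.
- **Drafting slip.** The milliseconds in the BRS definition suggest that R-R interval was meant. Probably so, but nothing elsewhere corrects it.
- **Common epochs.** Synchronised selections are meant to prevent bias. Matched longer windows keep that protection.

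**Conclusion.** The point holds, at moderate weight. As written, the BRS definition does not describe BRS, no HRV parameter is named, and averaging data within an epoch does not yield HRV. These findings need no assumption.

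The precision loss is a matter of degree, since the plan sets no precision target. Under the assumed spectra, one 30 s value has roughly 2 to 4 times the sampling CV of a 5 min value, and less of a disadvantage where several epochs are averaged. Between-day and between-person variation are not given, so the effect on actual power is unknown; the detectable differences above count window error alone.

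The documents do not support extending this to the primary or secondary analyses, the sample size or the false-positive rate.

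**What to change.** 1. In Table 2, define BRS as the change in R-R interval (ms) per mmHg change in systolic pressure, and state the estimation method (sequence, regression or spectral).
2. Name the HRV parameter. Compute it from ECG R-R intervals as a spread, and change the Table 3 rule for these two rows.
3. Keep 30 s epochs for mean values such as heart rate, middle cerebral artery velocity and the NIRS measures.
4. For HRV and BRS, pre-specify equal-length windows of up to about 5 min, at the same times relative to the stressor in both visits: for example the stressor itself and 0–5 min after it. Add an early-sitting baseline window in SMS and a pre-stress window in both visits, clear of the ultrasound breath-holds. If 5 clear minutes cannot be found before the stressor in CON, a common 2 min window still roughly halves the 30 s error (set B).
5. Before fixing the windows, reconcile two sets of passages. The CON sitting period is 20 min in section 2.3, but the section 2.6 timeline runs from −15 min to the stressor at −5 min. Pre-stress ultrasound is at −5 min in Tables 2 and 3, but at −15 to −5 min (CON) and −20 to −15 min (SMS) in the timelines. Post-stress ultrasound is at 20 min in section 2.3 and Table 2, at 25 min for CON in Table 3, and absent from the timelines.

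The cost is re-cutting data that will be recorded anyway and correcting Tables 2 and 3, with no added burden on participants. The downside is coarser time resolution for these two outcomes. A 5 min post-stress window may also not be stationary, and it cannot be longer without overlapping the next 5 min time point.
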